10.2.2 Adjudication committee

The role of the Adjudication Committee (AC) is to ensure that all treatment outcomes are judged uniformly, using standard criteria and processes. The AC will be composed of clinical experts to evaluate disease progression and harmonize endpoint assessment criteria using data provided by the sponsor.

Specific details regarding endpoint definitions can be found in the adjudication charter.

MAS adjudication committee

An independent Adjudication Committee will review and adjudicate information on all potential cases of MAS as long as adjudication for potential MAS cases is required as an additional pharmacovigilance activity according to adjudication committee charter. Potential cases will be identified through systematic database search of specified AE terms and/or (abnormal) laboratory criteria specified by the MAS adjudication committee. The Committee will review cases as they are identified. A report of the adjudication outcome will be provided to the Sponsor. As part of the adjudication process, a request for supplemental data collection will be sent to the investigator (as needed). If biological specimens (e.g., bone marrow aspirate, bronchoalveolar lavage, etc.) were collected as part of customary diagnostic workup, samples, such as tissue slides, may be requested by the committee for their review and/or for specialized analysis such as immunohistochemical staining CCI

Participants and parents will provide written informed consent for providing additional specimens. The MAS Adjudication Committee Charter provides detail on the committee composition, adjudication process, database AE and laboratory criteria search terms, and supplemental data package. The outcome of the adjudication will be reported on the MAS Adjudication CRF. The MAS Adjudication Committee Charter is available upon request.

11 Data Collection and Database management

11.1 Data collection

All data should be recorded, handled, and stored in a way that allows its accurate reporting, interpretation, and verification.

Designated investigator staff will enter the data required by the protocol into the Electronic Case Report Forms (eCRF). The eCRFs have been built using fully validated secure web-enabled software that conforms to 21 CFR Part 11 requirements. Investigator site staff will not be given access to the Electronic Data Capture (EDC) system until they have been trained. Automatic validation programs check for data discrepancies in the eCRFs, allow modification and/or verification of the entered data by the investigator staff.

The investigator/designee is responsible for assuring that the data (recorded on CRFs) (entered into eCRF) is complete, accurate, and that entry and updates are performed in a timely manner. The Investigator must certify that the data entered are complete and accurate.

After final database lock, the investigator will receive copies of the participant data for archiving at the investigational site.

All data should be recorded, handled, and stored in a way that allows its accurate reporting, interpretation, and verification.

11.2 Database management and quality control

Novartis personnel (or designated Contract Research Organization (CRO)) will review the data entered by investigational staff for completeness and accuracy. Electronic data queries stating the nature of the problem and requesting clarification will be created for discrepancies and missing values and sent to the investigational site via the Electronic Data Capture (EDC) system. Designated investigator site staff are required to respond promptly to queries and to make any necessary changes to the data.

Concomitant treatments and prior medications entered into the database will be coded using the World Health Organization (WHO) Drug Reference List, which employs the Anatomical Therapeutic Chemical classification system. Medical history/current medical conditions and AEs will be coded using the Medical Dictionary for Regulatory Activities (MedDRA) terminology.

Once all the necessary actions have been completed and the database has been declared to be complete and accurate, it will be locked and made available for data analysis. Any changes to the database after that time can only be made after written agreement by Novartis development management.

11.3 Site monitoring

Before study initiation, at a site initiation visit or at an investigator's meeting, a Novartis representative will review the protocol and data capture requirements (i.e. Electronic Source (eSource) DDE or eCRFs) with the investigators and their staff. During the study, Novartis employs several methods of ensuring protocol and GCP compliance and the

quality/integrity of the sites' data. The field monitor will visit the site to check the completeness of participant records, the accuracy of data capture / data entry, the adherence to the protocol and to GCP, the progress of enrollment, and to ensure that study treatment is being stored, dispensed, and accounted for according to specifications. Key study personnel must be available to assist the field monitor during these visits.

The investigator must maintain source documents for each participant in the study, consisting of case and visit notes (hospital or clinic medical records) containing demographic and medical information, laboratory data, electrocardiograms, and the results of any other tests or assessments. All information on CRFs must be traceable to these source documents in the participant's file. The investigator must also keep the original informed consent form signed by the participant (a signed copy is given to the participant).

The investigator must give the monitor access to all relevant source documents to confirm their consistency with the data capture and/or data entry. Novartis monitoring standards require full verification for the presence of informed consent, adherence to the inclusion/exclusion criteria, documentation of SAEs, and of data that will be used for all primary variables. Additional checks of the consistency of the source data with the CRFs are performed according to the study-specific monitoring plan. No information in source documents about the identity of the participants will be disclosed.

12 Data analysis and statistical methods

The statistical analysis of this study will be performed by Novartis. Any data analysis carried out independently by the investigator should be submitted to Novartis before publication or presentation.

The primary efficacy analysis will be based on the data up to the time when the first 11 participants have completed Week 28. Summary statistics for continuous variables will generally include n, mean, standard deviation, median, minimum, and maximum. For categorical variables, this will generally include frequency and percentage. For selected parameters, 25th and 75th percentiles will also be presented when applicable. Further details of the statistical considerations will be provided in the statistical analysis plan (SAP).

12.1 Analysis sets

The Full Analysis Set (FAS) and Safety set comprise all participants who received at least one dose of study treatment.

12.2 Participant demographics and other baseline characteristics

Demographic and other baseline data including disease characteristics will be listed and summarized descriptively for the FAS.

Relevant medical histories and current medical conditions at baseline will be summarized combined by system organ class and preferred term for the FAS.

12.3 Treatments

The duration of exposure in days to canakinumab treatment and the number of injections will be summarized by means of descriptive statistics using the safety set.

Prior and Concomitant medications will be summarized according to the Anatomical Therapeutic Chemical (ATC) classification system for the safety set. Significant non-drug therapies prior to and after the start of the study treatment will also be summarized.

12.4 Analysis supporting primary objectives

12.4.1 Definition of primary endpoint(s)/estimand(s)

The primary estimand is the response to treatment according to the adapted ACR 30 criteria at Week 8 excluding the effect of corticosteroid dose increase and/or intravenous administration of corticosteroid.

12.4.2 Statistical model, hypothesis, and method of analysis

The aim is to evaluate the treatment effect of canakinumab for Japanese AOSD participants on the adapted ACR 30 response at Week 8. The justification of the corresponding primary estimand are detailed in [Section 2.1](#).

The primary objective will be achieved if the null hypothesis is rejected at the 2.5% one-sided level of significance.

$H_0: p_{ACZ} \leq 0.40$ vs. $H_A: p_{ACZ} > 0.40$,

with p_{ACZ} being the proportion of participants who achieved adapted ACR 30 at Week 8.

Frequency tables with the number and percentage of participants who achieved adapted ACR 30 response together with a 95% confidence interval will be provided based on the FAS. A binomial test using the normal approximation will be performed and the Wald asymptotic confidence interval with continuity correction will be presented.

12.4.3 Handling of intercurrent events of primary estimand

The primary analysis will account for different intercurrent events as explained in the following:

1. **Systemic corticosteroid dose increase and/or iv corticosteroid use before Week 8 for any reason:** If a participant had corticosteroid dose increase and or iv corticosteroid use during the first 8 weeks after study treatment start, he/she will be considered as non-responder (non-responder imputation).
2. **Discontinuation of study treatment before Week 8 for any reason:** If adapted ACR 30 assessment at Week 8 is available, it will be included in the analysis.

Further details about the intercurrent events are provided in [Section 2.1](#).

12.4.4 Handling of missing values not related to intercurrent event

Missing adapted ACR 30 assessment at Week 8 will be imputed with non-responder regardless of the reason for missing data (non-responder imputation).

12.4.5 Supplementary analysis

The supplementary clinical question of interest is: What is the benefit of Canakinumab in Japanese AOSD patients to improve systemic and articular manifestation of AOSD regardless of systemic corticosteroid dose increase and/or intravenous administration of corticosteroid and regardless of treatment discontinuations for any reason? In this supplementary estimand, the population, primary variable and summary measure will be the same as the primary estimand, but the intercurrent event of corticosteroid dose increase and/or intravenous administration of corticosteroid will be ignored following a treatment policy strategy. The supplementary estimand will capture the effect of canakinumab regardless of increase in systemic corticosteroid dose and intravenous administration of corticosteroid, reflecting possibly the situation under clinical practice.

12.5 Analysis supporting secondary objectives

12.5.1 Key efficacy endpoint

The secondary estimand is the effect of canakinumab on oral corticosteroids tapering starting from Week 8 to Week 28. Successful tapering of corticosteroids will be derived on prednisone equivalent dose per day (mg/kg/day) as described in [Section 8.3.2](#). Further details will be described in the statistical analysis plan.

Frequency table with the number and percentage of participants who were able to taper oral corticosteroids successfully at Week 28 will be provided for the FAS. The participants who used systemic corticosteroid at baseline and were administered study treatment at Week 8 will be considered in this analysis.

The analysis will account for different intercurrent events as explained in the following:

1. Discontinuation of study treatment after Week 8 for any reason: If a participant early discontinued study treatment after Week 8 but had the Week 28 assessment regarding corticosteroid tapering, he/she will be included in the analysis.
2. Intravenous administration of steroid at any time between Week 8 and Week 28: If a participant had intravenous administration of steroid at any time between Week 8 and Week 28, he/she will be considered as corticosteroid tapering failure (non-responder imputation)

If the successful tapering of corticosteroids cannot be derived due to missing body weight, it will be imputed with the last available data from Week 8 to Week 28 (last observation carried forward (LOCF) approach).

12.5.2 Efficacy and/or Pharmacodynamic endpoint(s)

All efficacy endpoints will be summarized using the FAS.

Adapted ACR 30/50/70/90/100 response criteria

Frequency tables with the number and percentage of participants achieving the adapted ACR 30/50/70/90/100 criteria will be provided by scheduled visit.

Components of adapted ACR criteria

For the ACR individual components, summary statistics for the observed values and the change/percent change from baseline will be provided by scheduled visit.

Corticosteroid dose tapering

For oral corticosteroid dose, summary statistics for the change/percent change from baseline will be provided by scheduled visit after Week 8.

Rash

Frequency table with the number and percentage of participants in absent/present and typical or/and atypical if present will be provided by scheduled visit. The details on rash assessment are described in [Section 8.3.3](#).

DAS28-CRP

Summary statistics for the observed values and the change from baseline will be provided by scheduled visit.

Systemic feature score

For total score and, summary statistics for the observed values and the change from baseline will be provided by scheduled visit.

For each component score, the number and percentage of participants whose score is 1 will be provided by scheduled visit.

Total IL-1 β level

Total IL-1 β will be summarized by means of arithmetic and geometric mean, standard deviation (SD), coefficient of variation (CV) for arithmetic and geometric mean, median, minimum and maximum.

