## 1.2 Study objectives and endpoints

**Table 1-1 Objectives and related endpoints**

Objective(s)	Endpoint(s)
Primary objective(s)	Endpoint(s) for primary objective(s)

To evaluate the efficacy of canakinumab with respect to the adapted ACR 30 response after 8 weeks treatment

	

Proportion of participants who achieve adapted ACR 30 response at Week 8

Secondary objective(s)	Endpoint(s) for secondary objective(s)

To evaluate ability of canakinumab to taper corticosteroids based on success criteria starting from Week 8 to Week 28

To evaluate the efficacy of canakinumab with respect to the adapted ACR 30/50/70/90/100 response over time

To evaluate the efficacy of canakinumab on the systemic feature score over time

To evaluate the efficacy of canakinumab with respect to the components of adapted ACR criteria over time

To evaluate ability of canakinumab to taper corticosteroids dose over time after Week 8

To evaluate the efficacy of canakinumab on rash over time

To evaluate the efficacy of canakinumab on DAS28-CRP

To assess the safety and tolerability of canakinumab

	

Proportion of participants who are able to taper corticosteroids based on success criteria at Week 28.

Proportion of participants who achieved adapted ACR 30/50/70/90/100 response criteria at Day 15 and all subsequent visits.

Change from baseline in Systemic Feature Score (total score and each components) at Day 15 and all subsequent visits.

Change from baseline in each component of adapted ACR at Day 15 and all subsequent visits

Change from baseline of corticosteroid dose at all visits after Week 8.

Presence of rash (typical/atypical) at all visits during study.

Change from baseline in DAS28-CRP at Day 15 and all subsequent visits.

Incidence and severity of Treatment Emergent AEs. Proportion of participants up to end of study with:

Objective(s)	Endpoint(s)
	

- Adverse events

- Serious adverse events

- AEs related to study drug

- AEs leading to discontinuation

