

• To evaluate the pharmacokinetics (PK) / pharmacodynamic (PD) of canakinumab

	

• Means and mean change over time of:

-Vital sign parameters

-Laboratory parameters

• Canakinumab concentrations over time

• Total IL-1<math>\beta</math> (sum of IL-1<math>\beta</math> free and bound to canakinumab) level s over time

• To assess the immunogenicity of canakinumab

	

• Anti-canakinumab antibody identification and titer at BSL, Week 24, Week 48 and every 24 weeks until EOS.

Exploratory objective(s)	Endpoint(s) for exploratory objective(s)

Successful oral corticosteroids tapering is defined as meeting one of the following in terms of prednisone equivalent dose per day (mg/kg/day).

- Participants with prednisone equivalent dose of  $> 0.8$  mg/kg/day at baseline were able to reduce their dose to  $\leq 0.5$  mg/kg/day.
- Participants with prednisone equivalent dose from  $\geq 0.5$  mg/kg/day and  $\leq 0.8$  mg/kg/day at baseline were able to reduce their dose by at least 0.3 mg/kg/day.
- Participants with any initial prednisone equivalent dose at baseline were able to reduce their dose to  $\leq 0.2$  mg/kg/day.
- Participants with prednisone equivalent dose of  $\leq 0.2$  mg/kg/day at baseline were able to reduce their dose with any reduction.

AND maintaining a minimum adapted ACR30 response.

Details on how to calculate the prednisone equivalent dose per day are given in [Section 5.6.1](#).

Unless otherwise stated, the terms “prednisone equivalent dose” means prednisone equivalent dose of oral steroids.

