### **Corticosteroid dose tapering**

For oral corticosteroid dose, summary statistics for the change/percent change from baseline will be provided by scheduled visit after Week 8. The scheduled visits are defined as every 4 weeks through Week 48 and every 12 weeks thereafter.

The oral corticosteroid dose will be derived on prednisone equivalent dose per day (mg/day).

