## 2.14 Interim analysis

Two interim analyses will be performed after all participants have completed Week 28 to support the registration dossier, and Week 48 to supplement the dossier with long-term safety and efficacy data. At the interim analysis at Week 28, the primary efficacy analysis will be conducted based on the data up to the time when the first 11 participants have reached Week 28 (or prematurely discontinued prior to Week 28), that is 6Dec2022, CCI [REDACTED].

For the primary efficacy analysis with the first 11 participants, only the endpoints presented below will be analyzed.

- Participant demographics
- Baseline participant characteristics
- Adapted ACR 30/50/70/90/100 response at Week 8 (primary estimand)
- Subgroup analyses based on prior use of Tocilizumab
- Adapted ACR 30/50/70/90/100 response by visit

- Line plot of adapted ACR 30/50/70/90/100
- Successful oral corticosteroid tapering at Week 28
- Successful oral corticosteroid tapering by visit after Week 8
- Prednisone equivalent dose tapered to below 5 mg/day
- Oral corticosteroid dose (mg/day) by visit
- Each component of adapted ACR criteria by visit
- Rash by visit
- DAS28-CRP by visit
- DAS28-CRP response by visit
- EULAR response by visit
- Systemic feature score: Total score by visit
- Systemic feature score: Each component score by visit
- Ferritin level by visit
- Spaghetti plot of ferritin level by visit
- Number of tender/swollen joints
- Standardized CRP within normal range

The analysis set to be used in the analysis presented above will include up to about 11 participants.

After all participants have completed Week 28 and Week 48, two interim analyses will be performed on the efficacy and safety data during the study:

One will be at Week 28, to support the registration dossier and the other will be at Week 48 to supplement the dossier with long-term safety and efficacy data.

At the interim analyses, the data cut-off date for Week 28/Week 48 analysis will be the date of Week 28/Week 48 visit for the last participant. For efficacy analyses including PK/PD and biomarker-related analyses, the data up to Week 28/Week 48 visit for each individual participant will be included. For safety analyses and summaries for treatments, all available data will be included.

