## 5.6 Documentation of statistical methods

### 5.6.1 Calculation of prednisone equivalent dose (mg/kg/day) of oral steroids

The oral steroid dose at baseline will be the measurement on the date of baseline (Day 1) recorded on the concomitant medication page in eCRF. The oral steroid used for AOSD indication will be used. The oral steroid dose will be converted to prednisone equivalent dose using the conversion factor in [Table 5-2](#). The prednisolone equivalent dose will be derived by dividing the dose of the oral steroid dose by the corresponding conversion factor. Body weight will be the measurement at baseline (Day 1) or the last available weight before baseline.

The oral steroid dose at post-baseline assessment visits after Week 8 will be the measurement on one day before the date of corresponding assessment visits. Body weight will be the last available measurement on or before the date of steroid dose measurement.

The daily dose will be calculated by multiplying the conversion factors corresponding to the frequency recorded in eCRF (see [Table 5-3](#)). If participants use more than 2 oral steroids for AOSD on the same day, total dose per day will be used.

When a participant continued the study, if there is no concomitant oral steroid data at the assessment day, it will be considered as steroid free (0 mg).

If the oral steroid data is available but with missing information (e.g., body weight, frequency), the prednisone equivalent dose will be set to missing.

For example, if a participant weighs  $w$  kg and is taking  $x$  mg of Betamethasone 2 times per day and  $y$  mg of Hydrocortisone 3 times per day, the prednisone equivalent dose will be calculated as follows:

Prednisone equivalent dose per day =  $(x/0.12*2 + y/4*3)/w$ .

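### The by-visit corticosteroid dose summary counts oral steroid only and scores no oral record as 0 mg, so a continuing participant whose oral steroid is fully replaced by intravenous steroid on the reading day appears as a 100% reduction

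*Protocol*

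**What the plan says.** SAP Table 1-1, like Protocol Table 2-1, defines the endpoint as "Change from baseline of corticosteroid dose at all visits after Week 8", without a route. Protocol 12.5.2 analyses oral dose: "For oral corticosteroid dose, summary statistics for the change/percent change from baseline will be provided by scheduled visit after Week 8". SAP 2.7.2 does the same. SAP 1.2 adds that, unless otherwise stated, the prednisone equivalent dose "means prednisone equivalent dose of oral steroids".

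SAP 5.6.1 gives the derivation. The post-baseline dose "will be the measurement on one day before the date of corresponding assessment visits". The zero rule opens with the condition "When a participant continued the study" and goes on: "if there is no concomitant oral steroid data at the assessment day, it will be considered as steroid free (0 mg". It tests for the absence of an oral record, not for the absence of steroid.

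Intravenous steroid is handled in two places. For the primary endpoint, use before Week 8 is non-response (Protocol 2.1, SAP 2.5.1). For the key secondary endpoint, use between Week 8 and Week 28 is tapering failure at Week 28 (Protocol 2.2 and 12.5.1, SAP 2.6.1). For the remaining secondary endpoints, SAP 2.7.3 says only that missing values are not imputed and observed data are tabulated. SAP 2.7.2 schedules the oral dose table every 4 weeks to Week 48 and every 12 weeks after that.

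**The concern.** Replacing oral with intravenous steroid is not a reduction in corticosteroid use, yet the written rule turns it into the largest reduction possible. The plan foresees intravenous use: both estimands list it as an intercurrent event, and the prohibited-medication table (Protocol Table 6-3) names intra-articular, peri-articular and intramuscular corticosteroid but not intravenous. A participant given it may therefore stay in the study and in this table.

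Where baseline steroid is oral, leaving out a later intravenous dose can only make the reduction look larger. The table contributes to the steroid-sparing evidence at the Week 28 and Week 48 interim analyses, which support the registration dossier. With 11 or 14 participants, a single misclassified value is visible in a mean.

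**Working it through.** The documents give no figure for this endpoint, so there is none to reproduce. The check applies the SAP's rule to an illustrative case.

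**Inputs from the documents.** 14 participants for the secondary analyses (SAP 2.7.2); 11 for the primary efficacy cut (SAP 2.14); methylprednisolone conversion factor 0.8, used as a divisor (SAP 5.6.1, Table 5-2); permitted baseline dose 10 to 60 mg/day (Protocol 5.2, criterion 9).

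**Assumptions.** One participant has oral steroid fully replaced by intravenous steroid on the reading day and remains in the study. The intravenous dose is assumed, since the documents give none. All 11 or 14 participants are observed at that visit; with fewer, the shift is larger.

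**Score under the rule.** Percent change = 100 × (0 - baseline)/baseline = -100%, for any baseline above 0 and any intravenous dose.

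**Shift in the mean.** (scored change - actual change)/n.

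| Intravenous dose, in prednisone equivalent | Actual change | n = 14 | n = 11 |
|---|---|---|---|
| Equal to baseline | 0% | -100/14 = -7.1 points | -100/11 = -9.1 points |
| Twice baseline | +100% | -200/14 = -14.3 points | -200/11 = -18.2 points |

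**A case in mg.** Take 30 mg/day oral at baseline, replaced by intravenous methylprednisolone 40 mg/day.
- Prednisone equivalent: 40/0.8 = 50 mg/day.
- Scored change: 0 - 30 = -30 mg (-100%). Actual change: 50 - 30 = +20 mg (+66.7%).
- Shift with n = 14: (-30 - 20)/14 = -3.6 mg/day and (-100 - 66.7)/14 = -11.9 points.
- Shift with n = 11: -50/11 = -4.5 mg/day and -166.7/11 = -15.2 points.

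**Effect on a reported mean.** Suppose every other participant is at -50%. As written, the mean is (13 × -50 - 100)/14 = -53.6%, or (10 × -50 - 100)/11 = -54.5%. Counting the intravenous dose at a baseline-equivalent level gives (13 × -50 + 0)/14 = -46.4%, or (10 × -50 + 0)/11 = -45.5%.

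**Added rather than substituted.** If the participant above stays on 30 mg/day oral and the intravenous dose is added, the score is 0% although total exposure is 30 + 50 = 80 mg/day. The score is not -100%, but exposure is understated.

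**Reading day.** SAP 5.6.1 reads the dose one day before the visit but phrases the zero rule by the assessment day. If oral steroid stops and intravenous steroid starts on the visit day itself, the first reading returns the oral dose and the second returns 0 mg.

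**The case against.** The other side has a good deal to say.

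- *Oral-only is deliberate and labelled.* The key secondary question concerns oral tapering, and the output is titled as oral dose. This stands as far as the choice of variable goes. But the oral-tapering estimand still carries an intravenous failure rule, and nothing equivalent is visible for the dose table.
- *The -100% score needs a coincidence.* Intravenous steroid must wholly replace oral, on the one day read, in someone who stays in the study. This stands. Protocol 6.2.3 excludes rescue medication, and Protocol 9.1.1 makes leaving the study plausible for a participant with a serious event. Nothing in the documents shows that such a case is likely or has occurred.
- *The consequences are limited.* The table is untested, the median is planned (SAP 2.1), and SAP 2.4.2 summarises concomitant corticosteroids separately. These points limit the harm. The separate summary counts users and does not correct the dose at a visit.

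A reader might also infer that by-visit tapering success and "Prednisone equivalent dose tapered to below 5 mg/day" are left unprotected. The documents do not support that as a finding. Both appear in visible text only as list items in SAP 2.14, and their definitions may lie in blacked-out sections. By-visit success, if it follows the definition in SAP 1.2, also requires an adapted ACR30 response, which would keep many flaring participants from being counted as successes.

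**Conclusion.** The point holds for the by-visit oral dose summary. A stated rule assigns 0 mg and -100% to a continuing participant whose steroid has only changed route, and it ignores intravenous steroid given on top of oral. One full substitution moves the mean percent change by -7.1 points (n = 14) or -9.1 points (n = 11) if the intravenous dose equals baseline, and by more at higher doses. These sizes rest on one assumed participant at one visit, with no known frequency.

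It would go too far to say that anyone who receives intravenous steroid is counted as a complete responder, or that the steroid-sparing evidence as a whole is biased. The Week 28 success endpoint has its own failure rule, added intravenous steroid does not produce -100%, and no hypothesis test uses the dose table. The effect is on interpretation of a descriptive table, and it is worth correcting because correction is cheap.

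**What to change.** 1. In SAP 5.6.1, apply the 0 mg rule only when no systemic steroid of any route is recorded.
2. In SAP 2.7.2 and 5.6.1, derive the by-visit dose as total systemic prednisone equivalent; the Table 5-2 factors are listed by medication and can be used. State whether the restriction to steroid given for AOSD is kept. At minimum, keep the oral-only table but flag intravenous users and do not score them as 0 mg.
3. Align Protocol 12.5.2 with the endpoint wording, and record the change in SAP Section 4, which now lists none.
4. Reconcile the two reading days in SAP 5.6.1.
5. For by-visit tapering success and the below 5 mg/day output in SAP 2.14, carry over the Week 28 intravenous failure rule if the blacked-out sections do not already do so.

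The cost is wording and one derivation; concomitant medications are already collected (Protocol 6.2.1). There are two drawbacks. A pulse dose can dominate a mean, so the planned median should be read alongside it. A single-day reading will still miss intravenous courses given between visits, so a flag for any intravenous use since the previous visit would be a useful addition. No treatment rule changes.
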